Posaconazole prophylaxis during anti-thymocyte globulin treatment for hypoplastic myelodysplastic syndrome(HMDS)/ aplastic anemia(AA) patients

Trial Registration: Clinicaltrials.gov NCT03318159, registered Jul 23, 2017

Document Date: November 4, 2024

Methods

Study Design

In this prospective, open label, single arm study(Clinicaltrials.gov no. NCT03318159), we enrolled patients with diagnosed hypoplastic myelodysplastic syndrome(HMDS) and aplastic anemia(AA) patients who received anti-thymocyte globulin(ATG) treatment at Seoul National University Hospital(SNUH) and Seoul National University Bundang Hospital from Aug 2018 through Jun 2023. All patients enrolled in the study provided written informed consent. Inclusion criteria were as follows : 1) ≥ 18 years and < 75 years old, 2) hypoplastic myelodysplastic syndrome(HMDS) or aplastic anemia(AA) diagnosed, 3) anti-thymocyte globulin(ATG) treatment, 4) no QTc prolongation on initial ECG, 5) Serum creatinine and AST/ALT levels ≤ 2 times the upper limit of the reference range for laboratory and 6) Serum bilirubin levels ≤ 1.5 times the upper limit of the reference range for laboratory. Exclusion criteria were as follows : 1) Suspected fungal infection within 30 days of ATG treatment, 2) history of allergic to -triazoles, 3) diagnosis of other malignancy in the previous 5 years, 4) previous chemotherapy, radiation, or immunosuppressive treatment, 5) pregnant or breastfeeding, male or female patients of reproductive potential who are not employing an effective method of birth control, 6) active HBV and HCV patients and HIV positive patients, 7) history of receiving organ transplantation, 8) QTc prolongation is identified on baseline ECG of who have Torasdes de pointes syndrome and 9) on ergotamine alkaloids, CYP3A4(terfenadine, astemizole, cisapride, pimozide, halofantrine, quinidine) or HMG-CoA reductase inhibitors.

Patients received 300mg Posaconazole orally twice daily on day 1 and 300mg once daily for 4weeks from day 2. Posaconazole should start on the same day as ATG, but if it's not possible to start on the same day, it's allowed to start within $+/ - 3$ days.

The primary end point was the incidence of proven/probable/possible fungal infection through 4-week post-treatment period, and the secondary end points were overall survival, any fungal infection.

Patients were followed up for 6 months from the end of prophylactic treatment for the occurrence of additional fungal infection and survival, respectively.

The determination of sample size

The incidence rate of invasive fungal infection is estimated to be 80% in childhood aplastic anemia patients undergoing ATG treatment (Pediatric Hematology and Oncology, 31:1, 20-28, 2014). Allowing for up to a rate of 30%, based upon a sample size of n=20 patients per group, this study will ensure that a two-sided test with $\alpha = 0.05$ has 80% to detect the difference. We aim to recruit double the minimally required sample size.

Statistical Analysis

Categorical variables were compared using Student t-test or Pearson's chi-square test as appropriate. $P < 0.05$ are considered statistically significant. Overall survival were evaluated by Kaplan-Meier analysis.

Ethical Considerations

This study was approved by the institutional review board at Seoul National University Hospital(IRB; 1706-207-866) and was conducted in accordance with the guidelines of the Declaration of Helsinki for biomedical research. Informed consent was obtained from all participants.

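### Does the loosely worded four-week post-treatment window leave the primary infection rate undefined, or understated for patients who stop posaconazole early?

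*Combined protocol and SAP*

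**What the plan says.** The Study Design section gives the primary end point: "The primary end point was the incidence of proven/probable/possible fungal infection through 4-week post-treatment period". Its dosing sentence fixes the planned course: "Patients received 300mg Posaconazole orally twice daily on day 1 and 300mg once daily for 4weeks from day 2". On timing relative to anti-thymocyte globulin (ATG) it says "Posaconazole should start on the same day as ATG", with three days' leeway either way.

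Follow-up is described once: "Patients were followed up for 6 months from the end of prophylactic treatment for the occurrence of additional fungal infection and survival, respectively". The other end points are listed as "the secondary end points were overall survival, any fungal infection". The Statistical Analysis section adds only "Overall survival were evaluated by Kaplan-Meier analysis" and is silent on the infection window.

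The sample-size section sets 80% against 30% with 20 per group, and then states "We aim to recruit double the minimally required sample size", which is 40 if the minimum is 20.

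**The concern.** Both posaconazole and ATG could be the treatment in question. The sentence does not say whether counting stops four weeks after the planned end or the actual end, and it gives no opening day. If the window follows each patient's own last dose, someone who stops early is observed for less time than someone who completes, and infections after the shorter window are not counted. The crude rate would then be too low against a fixed day, and too low is the favourable direction for a prophylaxis study.

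Other literal readings give different rates from the same data: only the four weeks after the last dose, four weeks from the start, or four weeks after ATG ends. The document is dated November 2024 and enrolment ended in June 2023, so an unfixed window could be settled once results are known. That is a risk; nothing in the documents suggests it happened.

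**Working it through.** **1. The closing day.** The plan states no closing day, so it has to be derived. The planned last dose is day 1 + 28 = day 29. Four weeks more gives 29 + 28 = day 57.

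**2. Which reading the text supports.**
- *First dose to four weeks after prophylaxis ends.* The end point runs *through* the post-treatment period, which ordinarily includes the time before it. The only end date the plan uses for follow-up is the end of prophylaxis. Calling later infections *additional* implies that earlier ones already count. A completer closes on day 57.
- *The same, with the planned end.* The text describes a fixed course and never mentions an actual last dose. Everyone closes on day 57.
- *Only the four weeks after the last dose.* This conflicts with *through* and with *additional*.
- *Four weeks from the start.* This conflicts with the ordinary meaning of post-treatment.
- *Four weeks after ATG ends.* This is possible, because the plan also calls ATG a treatment, but no follow-up is tied to the end of ATG and its length is not given.

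At an assumed 57-day risk of 30%, constant hazard and no early stopping, the last three give:
- post-dose weeks only: 0.7^(29/57) − 0.7 = 0.834 − 0.700 = 13.4% of dosed patients;
- from the start: 1 − 0.7^(28/57) = 16.1%;
- after ATG: 1 − 0.7^((k+28)/57) = 16.6% to 21.2% for an assumed ATG course of k = 1 to 10 days.

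The apparent 13-30% spread therefore comes from readings that the text disfavours, or from an ATG length that has to be assumed.

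**3. The early-stopper effect, if the actual last dose governs.** A patient whose last dose is on day L is counted to day L + 28. Stops on days 1-28 close on days 29-56; stops on days 7, 14 and 21 close on days 35, 42 and 49. The documents give no stop days or stopping rate, so all of these are assumptions.

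For true 57-day risk p and constant hazard, the counted risk is q(L) = 1 − (1 − p)^((L+28)/57). With a share f stopping on day L, the shortfall is f × (p − q).

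| p | L | q(L) | f = 10% | f = 30% |
|---|---|---|---|---|
| 30% | 7 | 19.67% | 1.03 points, 0.41 of 40 | 3.10 points, 1.24 of 40 |
| 30% | 21 | 26.41% | 0.36 points, 0.14 of 40 | 1.08 points, 0.43 of 40 |
| 10% | 7 | 6.26% | 0.37 points, 0.15 of 40 | 1.12 points, 0.45 of 40 |

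Half of all patients stopping on day 7 at p = 30% gives 0.5 × (30 − 19.67) = 5.2 points, or 2.1 of 40.

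**4. Other hazard shapes, p = 30%, 30% stopping on day 7.**
- *Front-loaded.* Put 75% of the cumulative hazard H = −ln 0.70 = 0.3567 in days 1-29. By day 35 the cumulative hazard is 0.75H + 0.25H × 6/28 = 0.2866. The gap is exp(−0.2866) − 0.700 = 0.0508, and 0.3 × 0.0508 = 1.5 points, or 0.6 of 40.
- *Hazard doubled after stopping.* With λ = 0.3567/57 = 0.006257, survival free of infection is exp(−63λ) = 0.674 at day 35 (7 + 2 × 28 = 63) and exp(−107λ) = 0.512 at day 57 (7 + 2 × 50 = 107). The gap is 0.162, and 0.3 × 0.162 = 4.9 points, or 1.9 of 40.

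**5. Yardsticks.** The exact 95% interval for 12 of 40 is 16.6-46.5%, about 13 points below and 16 above the estimate. The planned contrast is 50 points. The sample size takes only the two rates, alpha and power: a two-sided two-proportion formula with continuity correction gives 19 per group against the stated 20. Window length does not enter it.

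**6. Whether data are lost.** Six months (about 182 days) from the end of prophylaxis takes even a day-1 stopper to about day 183, so follow-up as described covers day 57.

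**The case for a change.** The strongest case for a change is that the primary end point of a single-arm trial should leave nothing to interpretation, and here one sentence would settle it. The ambiguity is on the face of the text and is not the result of redaction or a broken table. Actual and planned end of prophylaxis both remain open, and they differ for any early stopper. The calculations above are not bounds: they rest on assumed stop days, and stopping might itself raise the risk more than the doubling tried here. Stating the window openly would also remove any suspicion that it was chosen late.

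Much of this stands. The window is underspecified, a last-dose window can only lower the rate against a fixed day 57 (unless prophylaxis continued past day 29), and the wording could be better. What does not follow is that the result is at risk. The bias needs one particular reading together with early stopping that the documents do not report. The remedy has its own cost: fixing a new primary window after enrolment closed is itself a post hoc definition, and it would have to be shown beside the intended one. Coverage to day 57 also assumes that early stoppers stayed in follow-up, which the plan implies but does not state.

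The related points add little. The six-month follow-up sentence supplies a period for later fungal infections, if only by implication. The unstated origin of the Kaplan-Meier curve is a separate matter: under constant hazard a curve started at the end of prophylaxis carries no bias, and nothing says that deaths on prophylaxis were left out. A competing-risk estimate equals the simple proportion if everyone is followed to day 57.

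**Conclusion.** No change to the plan follows. The end point leaves its window to be inferred, but the surrounding text points to the first posaconazole dose through four weeks after prophylaxis ends. That closes on day 57 for every completer, and for every patient if the planned end is meant. An analyst would reach this without strain.

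The remaining uncertainty concerns early stoppers under an actual-last-dose rule. At an assumed 30% risk with constant hazard and 10-30% stopping on day 7, it amounts to 0.4-1.2 infections in 40. It is smaller with later stops, lower risk or front-loaded infections, and about 2 in 40 if half the patients stop on day 7 or if stopping doubles the hazard. All of these are below sampling error and far below the 50-point planned difference. The conclusion would weaken only if early stopping proved very common and infections clustered late after stopping, and the documents give no sign of either.

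### The sizing text implies a test against an 80% rate in children with aplastic anemia; in this single-arm adult AA/HMDS trial a significant result could not be attributed to posaconazole

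*Combined protocol and SAP*

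**What the plan says.** Under the sample-size heading, the benchmark is "The incidence rate of invasive fungal infection is estimated to be 80% in childhood aplastic anemia patients undergoing ATG treatment". It is set against a rate of up to 30%, and the planned size is justified with the words "based upon a sample size of n=20 patients per group, this study will ensure that a two-sided test with". The significance level is 0.05, and the promise made for that comparison is that it "has 80% to detect the difference". On recruitment, the section adds: "We aim to recruit double the minimally required sample size".

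The Study Design section describes a different setting. The trial is introduced with "In this prospective, open label, single arm study", and the first two inclusion criteria are "≥ 18 years and < 75 years old, 2) hypoplastic myelodysplastic syndrome(HMDS) or aplastic anemia(AA) diagnosed". Patients with a suspected fungal infection within 30 days of ATG are excluded. The endpoint is stated as "The primary end point was the incidence of proven/probable/possible fungal infection through 4-week post-treatment period".

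The Statistical Analysis section says only "Categorical variables were compared using Student t-test or Pearson's chi-square test as appropriate", with a 0.05 significance threshold and Kaplan-Meier analysis for survival. It sets no null rate and names no comparator for the primary endpoint.

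**The concern.** A test that detects a difference needs two rates. The trial supplies one, and the only candidate for the other is the paediatric 80%. With a single arm, that external figure would have to stand in for what these patients would have experienced without posaconazole.

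The document gives no reason why it should. The reference patients are children and the trial's are aged 18 to under 75. The reference disease is aplastic anemia, whereas the trial also takes HMDS. The trial removes patients with recent suspected fungal infection. The reference rate is for invasive infection, while the endpoint counts proven, probable and possible infection over a set window, and the document does not show that the definitions or windows match. No adult rate, matched historical cohort or adjustment is described.

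If the implied test were run and came out significant, it would naturally be read as a reduction due to the drug. The design cannot separate that from a background rate in these adults that differs from 80% for other reasons.

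**Working it through.** **Inputs from the sample-size section.** Reference rate 0.80; target rate 0.30; two-sided alpha 0.05; power 80%; 20 per group; recruitment double the minimum. I infer n=40 as twice 20.

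**Input not in the document.** The background infection rate in adults with AA/HMDS on ATG. I assume 50%, 60% and 70%.

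**Step 1: reproduce the 20.** For two groups with pooled variance, the mean rate is 0.55 and

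n = [1.960·√(2·0.55·0.45) + 0.842·√(0.80·0.20 + 0.30·0.70)]² / (0.80 − 0.30)² = (1.379 + 0.512)² / 0.25 = 14.3, so 15 per group.

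With continuity correction, n′ = (14.3/4)·[1 + √(1 + 4/(14.3·0.50))]² = 18.1, so 19 per group, close to the stated 20.

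An exact one-sample test of 80%, with at most 0.025 in the lower tail, first reaches 80% power against 30% at n=8: reject at 3 or fewer infected, lower tail 0.010, power 0.806. The 20 therefore looks like a two-group calculation in which 80% was treated as a comparison group. If the 30% is instead read as a 30-point drop (80% to 50%), the one-sample normal approximation gives 17 and the two-group formula 39. On every reading, 80% is the reference.

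**Step 2: rejection limits for an exact one-sample test of 80%.** Find the largest count c with P(X ≤ c | n, 0.80) ≤ 0.025.

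- n=40: c=26 (lower tail 0.0194; 27 would give 0.0432).
- n=20: c=11 (lower tail 0.0100; 12 would give 0.0321).

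**Step 3: chance of a significant result below 80% if the drug does nothing.** This is P(X ≤ c | n, p), with p the assumed adult background rate.

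| Test | n | c | p=50% | p=60% | p=70% | p=80% |
|---|---|---|---|---|---|---|
| Exact one-sample, 0.025 lower tail | 40 | 26 | 0.98 | 0.79 | 0.30 | 0.019 |
| Exact one-sample, 0.025 lower tail | 20 | 11 | 0.75 | 0.40 | 0.11 | 0.010 |
| Exact one-sample, minimum-likelihood two-sided | 20 | 12 | 0.87 | 0.58 | 0.23 | 0.032 |
| Two-group Pearson, uncorrected, against a hypothetical 32/40 | 40 | 23 | 0.87 | 0.43 | 0.06 | 0.001 |
| Two-group Pearson, uncorrected, against a hypothetical 16/20 | 20 | 10 | 0.59 | 0.24 | 0.05 | 0.003 |

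The minimum-likelihood test rejects at 12/20 (p=0.044). At n=40 it has the same limit, 26, as the first row. The Pearson limits are 23/40 against 32/40 (p=0.030; 24/40 gives 0.051) and 10/20 against 16/20 (p=0.047; 11/20 gives 0.091).

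**Step 4: reading the table.** Doubling recruitment does not help: within each type of test, the larger n gives the higher chance of rejecting 80% at each assumed rate below it. At an adult rate of 80%, no test in the table exceeds 0.032, and the chance falls further above 80%.

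**The case against.** The strongest reply is that no test against 80% is actually planned. The primary endpoint is a descriptive incidence, the 80% appears only in the sizing text, and nowhere does the document say that a reduction will be claimed or credited to posaconazole. The harm then needs two further steps: someone runs the test, and someone reads it causally. This stands, and it makes the point conditional. It does not remove it, because the sizing text does promise a test to detect the difference and the plan sets a significance threshold.

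It is also fair that any single-arm trial has limited attribution and that many use historical rates. The point specific to this trial is narrower: the rate comes from children and no argument carries it over to the adults enrolled.

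The magnitudes rest on assumed adult rates, all below 80%, and on a test the plan does not name. The two-group rows need a comparison group that does not exist. The table illustrates a qualitative point and does not estimate the trial's error rate.

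A reader might go further and infer that 80% is too high for adults, that the cited children had no antifungal prophylaxis, or that a background difference is as likely an explanation as a drug effect. The document supports none of these. It gives no adult rate, does not describe the children's prophylaxis, and offers no basis for weighing the two explanations. If the adult background rate were above 80%, the benchmark would be conservative.

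**Conclusion.** The point holds as a conditional limit on interpretation. The sizing text implies a two-sided 0.05 test of the observed incidence against a paediatric 80% that the document does not justify for adults with AA or HMDS. If that test is run, a significant result below 80% could not be attributed to posaconazole.

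The size and direction of any bias are unknown. With an inert drug, the chance of a significant result across the tests tabulated is 0.59 to 0.98 at an assumed adult rate of 50%, 0.24 to 0.79 at 60%, and 0.05 to 0.30 at 70%. These ranges assume n=20 or n=40. At 80% or more, a false claim is unlikely.

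It would be wrong to read this as a flaw in the incidence data. The observed incidence under prophylaxis remains a valid description; only the comparison with 80% fails. The matter should be settled before results are interpreted.

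**What to change.** Report the primary incidence with an exact (Clopper-Pearson) 95% confidence interval. For example, 6/40 would give 15% (5.7% to 29.8%) and 3/20 would give 15% (3.2% to 37.9%); these counts are hypothetical. Limit the conclusion to incidence under prophylaxis in adults with AA/HMDS. Make no claim of a reduction from the paediatric 80% and give no p-value against it.

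State as limitations the differences in age and disease, and that comparability of the endpoint definition and observation window with the reference figure is undocumented.

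Enrolment ran from August 2018 through June 2023 and the document is dated November 2024, so the change must be labelled post hoc. It needs no further patients, only analysis and reporting wording. The price is a more modest efficacy claim.

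### The size of this single-arm study is justified as 20 patients per group with 80% power; read literally as 80% versus 30%, neither figure is that of the one-arm test

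*Combined protocol and SAP*

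**What the plan says.** The Study Design section calls this a "prospective, open label, single arm study" and defines its main outcome as a single proportion: "The primary end point was the incidence of proven/probable/possible fungal infection through 4-week post-treatment period". Patients were enrolled "from Aug 2018 through Jun 2023".

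The section on determination of sample size starts from an infection rate "estimated to be 80% in childhood aplastic anemia patients undergoing ATG treatment", taken from one published paper. The rate set against it is worded "Allowing for up to a rate of 30" (per cent). The size is then given in the words "based upon a sample size of n=20 patients per group, this study will ensure that a two-sided test with", and the significance level follows as 0.05. About the performance of that test, the plan says only that it "has 80% to detect the difference"; the word power is absent but clearly meant. The section ends "We aim to recruit double the minimally required sample size", with no number.

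The Statistical Analysis section lists the t-test, Pearson's chi-square and Kaplan-Meier. It does not mention the 80% reference rate, a one-sample test, or a confidence interval for the primary incidence.

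**The concern.** A per-group size implies two groups, and the documents describe one. The two diagnoses, hypoplastic MDS and aplastic anemia, cannot be the groups, because 80% against 30% is a contrast between a literature rate and a rate on prophylaxis, not between diagnoses.

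Three things follow for the reader. The stated power may belong to a test this design cannot perform. The recruitment target is defined as twice a minimum that may not be the minimum for this design, and it is never written as a number. The comparison used to size the study also has no counterpart in the analysis section. What is at stake is whether the stated basis can be checked and reported correctly. The number of patients is not in question, because enrolment closed in June 2023 and the document is dated November 2024.

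**Working it through.** **Inputs, all from the sample-size section:** reference rate 0.80; 30%, read either as the rate under prophylaxis (0.30) or as a 30-point reduction (0.80 − 0.30 = 0.50); two-sided alpha 0.05 (z = 1.960); power 80% (z = 0.842); n = 20 per group.

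**1. Can the figure of 20 be reproduced?**

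*Two groups, 0.80 versus 0.30.* The mean rate is 0.55.
- n = [1.960·√(2·0.55·0.45) + 0.842·√(0.80·0.20 + 0.30·0.70)]² / 0.50² = 14.3, so 15 per group.
- With continuity correction: (14.3/4)·[1 + √(1 + 4/(14.3·0.50))]² = 18.1, so 19 per group.
- Fisher's exact test: power 79.2% at 17 per group, 83.5% at 18, 84.6% at 20. The minimum is 18.

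*One arm, 0.80 versus 0.50.*
- n = [(1.960·√(0.80·0.20) + 0.842·√(0.50·0.50)) / 0.30]² = 16.1, so 17.
- With continuity correction: (16.1/4)·[1 + √(1 + 2/(16.1·0.30))]² = 19.3, so 20.
- The exact binomial test first reaches 80% at n = 19 (82.0%).

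Both routes arrive at or near 20, so the arithmetic does not identify which one was used. As a cross-check, two groups of 20 with 0.80 versus 0.50 have only 40.9% power (Fisher), so that combination can be set aside.

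**2. What does one arm of 20 deliver?** Exact binomial, X = number infected, reference 0.80. The reference-rate tails are P(X ≤ 11) = 0.0100, P(X ≤ 12) = 0.0321 and P(X = 20) = 0.0115.

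| Two-sided convention | Reject at or below | Total size | Power at 30% | Power at 50% |
|---|---|---|---|---|
| 0.025 per tail | 11 | 0.0215 | 99.5% | 74.8% |
| Minimum-likelihood | 12 | 0.0437 | 99.9% | 86.8% |

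At a rate of 30% the stated 80% is far below the actual power. At 50% the two conventions lie on either side of it.

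**3. What is the one-arm minimum for 80% versus 30%?**
- n = 8: reject at 3 or fewer, lower tail 0.0104, power 80.6% under both conventions.
- n = 7: the minimum-likelihood test also rejects at 3 or fewer (0.0333), power 87.4%.
- With 0.025 per tail, power stays above 80% at every n from 8 to 80.
- Normal approximation: 5.5, so 6; with continuity correction 7.3, so 8.

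On the literal reading, 20 is more than twice what this test needs.

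**4. The doubled target.** With one group, 2 × 20 = 40. Only if a second group had been counted would it be 2 × 2 × 20 = 80. At N = 40 the exact test has lower rejection limit 26 (P(X ≤ 26) = 0.0194; P(X ≤ 27) = 0.0432), with power above 99.9% at 30% and 98.1% at 50%. For scale, 12 infections in 40 (30%) would have an exact 95% interval of 16.6% to 46.5%.

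**The case against.** The strongest reply is that per group is loose wording in what was really a one-arm calculation. If 30% meant a 30-point reduction, the continuity-corrected one-sample formula gives exactly 20, a better match than the two-group 18 or 19. This stands as a real possibility. A reader might infer that the study was sized as a two-group trial, and the text does not prove that. Against it, the plan speaks of a rate of 30%, which reads more naturally as the rate itself, and per group remains wrong for one arm on either reading.

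A second reply is that ensuring 80% can mean at least 80%, which 99.5% satisfies. That is fair for the power claim. It does not rescue the statement that 20 is the minimum.

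A third concerns the target. A reader might infer that the planned total was just as likely 80 as 40. The documents contain only one group, so 40 is the natural reading, and 80 requires counting a group that appears nowhere. Doubling a recomputed one-arm minimum of 8 would give 16, but that replaces the plan's own figure. What remains is that the total should have been written down.

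Finally, the missing interval for the primary endpoint is a gap in the analysis plan rather than an arithmetical error, and Pearson's chi-square does have a one-sample form. Both points are right. The gap is secondary here, and an exact test is a suitable choice, not the only valid one.

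**Conclusion.** The point holds in this form: the per-group basis contradicts the single-arm design, and under the literal 80% versus 30% the stated power and minimum size are not those of the one-arm test (99.5% or 99.9% instead of 80%; 7 or 8 patients instead of 20). This rests on treating 80% as a fixed reference, on two-sided alpha 0.05, and on reading the unlabelled 80% as power.

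A reader might infer that the study is underpowered. On the plan's own 80% and 30% the opposite is true. Only if 30% means a drop to 50% does one arm of 20 sit near 80% power, and a total of 40 would then still give 98.1%. The origin of 20 stays open. Whether the recruitment target was met cannot be judged here, because neither a numeric target nor actual enrolment is given. The correction is worth making, but its consequence is confined to the stated rationale and the reporting.

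**What to change.** Keep the plan's sample-size statement on record as written and add a note covering the following:

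- The per-group basis does not match the single-arm design.
- Whether 30% is the rate under prophylaxis or a 30-point reduction.
- The planned total as a number: 40 on the single-arm reading, 80 only if a second group had been counted.
- The power restated for a one-sample test against 80%, naming the two-sided convention and marked as specified after enrolment ended.

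In the Statistical Analysis section, make the observed incidence of the primary endpoint with an exact (Clopper-Pearson) 95% confidence interval the main result. The t-test and a between-group chi-square do not match the one-sample comparison used for sizing. If a comparison with 80% is reported, an exact binomial test is a suitable choice. Restating the power does not justify 80% as the reference: that rate is for invasive infection in children, whereas this study enrols adults and counts possible infections too.

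Cost: a few sentences in two sections and no extra patients.

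### The analysis methods named do not fit a single-arm binary primary endpoint: the incidence gets no confidence interval and no one-sample test against the 80% reference rate.

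*Combined protocol and SAP*

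**What the plan says.** The Study Design section calls the trial a "prospective, open label, single arm study" and defines one binary outcome: "The primary end point was the incidence of proven/probable/possible fungal infection through 4-week post-treatment period". It adds that "the secondary end points were overall survival, any fungal infection".

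The sample-size section supplies a reference rate: "The incidence rate of invasive fungal infection is estimated to be 80% in childhood aplastic anemia patients undergoing ATG treatment". It sets this against a rate of up to 30%, with 20 patients per group, and says "this study will ensure that a two-sided test with" alpha 0.05 has 80% power. It then adds "We aim to recruit double the minimally required sample size".

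The Statistical Analysis section has three sentences. The first is "Categorical variables were compared using Student t-test or Pearson's chi-square test as appropriate". The second sets the significance threshold at P < 0.05. The third assigns Kaplan-Meier to overall survival. None of them mentions the primary endpoint, an interval, a one-sample test or the 80% rate.

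**The concern.** With no control arm, the primary result is one proportion. It can be estimated with an interval, or tested against a fixed rate. The named methods do neither: they compare groups, and the design has no groups for the primary endpoint. The t-test is a method for means, so Pearson's chi-square is the only suitable test named for categorical data.

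The sample-size paragraph shows that a test of some kind was intended, but the analysis section does not say which test, or against what value P < 0.05 is to be judged. Followed as written, the plan gives a percentage without a statement of precision. The secondary endpoint of any fungal infection has the same gap, because Kaplan-Meier is assigned to survival only.

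**Working it through.** **Inputs.** Reference rate 80%, expected rate 30%, two-sided alpha 0.05, power 80% and n = 20, all from the sample-size section. The recruitment target is double the minimum; I read it as 40 if 20 is the minimum, and show both.

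**1. The plan's own sample size.** For two groups, with mean rate 0.55:

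n₀ = [1.960·√(2·0.55·0.45) + 0.842·√(0.8·0.2 + 0.3·0.7)]² / 0.5² = (1.379 + 0.512)² / 0.25 = 14.3

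With continuity correction, n = (n₀/4)·[1 + √(1 + 4/(0.5·n₀))]² = 18.1, so 19 per group, close to the stated 20. A one-sample calculation against 80% gives 6 (normal approximation) or 8 (exact binomial, power 80.6%). The stated figure therefore fits a two-group comparison, which this design cannot make.

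**2. The missing interval.** Clopper-Pearson limits for x events in n are the 2.5% point of Beta(x, n−x+1) and the 97.5% point of Beta(x+1, n−x).

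- 6/20 (30%): 11.9% to 54.3%, width 42.4 points (Wilson 14.5% to 51.9%, width 37.3).
- 12/40 (30%): 16.6% to 46.5%, width 30.0 points (Wilson 18.1% to 45.4%, width 27.4).

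**3. Testing 80% at the expected rate.** One-sample Pearson: X² = (x − 0.8n)² / (n·0.8·0.2).

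- 6/20: X² = 100/3.2 = 31.25, p = 2.3×10⁻⁸; equal-tailed exact p = 3.7×10⁻⁶.
- 12/40: X² = 400/6.4 = 62.5, p = 2.7×10⁻¹⁵; equal-tailed exact p = 2.3×10⁻¹¹.

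Both tests reject 80%, so near 30% the choice of test does not matter.

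**4. Where the choice could matter.** The next table supposes that Pearson's test is used as a one-sample test against 80%. Size is the binomial probability, at a true 80%, of the counts that reject. The 60% column is an assumed true rate.

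| n | Test | Rejects at | Size | Power at 60% |
|---|---|---|---|---|
| 20 | Pearson | ≤12 or 20 | 0.044 | 0.58 |
| 20 | Exact, probability-ordered | ≤12 or 20 | 0.044 | 0.58 |
| 20 | Exact, equal-tailed | ≤11 or 20 | 0.022 | 0.40 |
| 40 | Pearson | ≤27 or ≥37 | 0.072 | 0.87 |
| 40 | Exact, probability-ordered | ≤26 or ≥37 | 0.048 | 0.79 |
| 40 | Exact, equal-tailed | ≤26 or ≥38 | 0.027 | 0.79 |

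At 27/40, Pearson gives X² = 25/6.4 = 3.91, p = 0.048. The exact p is 0.086 equal-tailed (2 × 0.0432) or 0.072 probability-ordered, and the Clopper-Pearson interval is 50.9% to 81.4%. Pearson would declare a rate below 80% where neither exact test does.

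At 12/20, Pearson gives p = 0.025 and the probability-ordered exact test p = 0.044, so they agree. Only the equal-tailed version (p = 0.064, interval 36.1% to 80.9%) does not reject.

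**The case against.** The 80%, the 30% and the two-sided 0.05 level stand directly above the analysis section, so a reader can infer the intended comparison. An interval can be computed at any time from the count and the denominator, and at 30% no conclusion changes. The quoted sentence may have been meant only for baseline or subgroup comparisons.

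Much of this stands. The comparator is in the document, and the result against 80% is secure at the expected rate. But if the sentence was meant for other comparisons, the primary endpoint has no stated method at all.

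A reader might go further and infer that Pearson's test inflates the type I error at these sample sizes. The documents do not support that. They never say that a one-sample chi-square will be used; that reading is supplied here to see what it would imply. Even then its size exceeds 0.05 at only 7 of the 21 sample sizes from 20 to 40. At 20 its decisions match those of a valid exact test. If the true rate is 30%, the chance of a count on which Pearson and the equal-tailed test disagree is about 0.4% at n = 20 and about one in a million at n = 40.

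**Conclusion.** The concern holds as a mismatch between the stated methods and the primary endpoint. The named comparisons cannot analyse a one-arm incidence, and neither an interval nor a one-sample test connects the result to the rate on which the study was sized. At the expected 30% the missing interval spans 30 to 42 points, and supplying it is the main gain. An effect on the test decision arises only for rates much nearer 80%, and only if Pearson's test were used in one-sample form.

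The figures assume 20 or 40 analysed patients and a fixed 80% reference. Whether a childhood rate suits adults is a separate question. The document is dated after enrolment ended, and a reader might infer that the analysis was chosen once results were known. The text does not show whether an earlier dated version fixed the method, so no such conclusion is drawn.

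**What to change.** Replace the sentence on categorical variables with text to this effect:

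> The primary endpoint is reported as the number of patients with proven, probable or possible fungal infection in the primary window, divided by all patients who started posaconazole [sponsor to confirm the denominator], with a two-sided Clopper-Pearson 95% confidence interval. If a test is reported, it is the two-sided equal-tailed exact one-sample binomial test at 0.05 against the 80% reference rate. Any fungal infection is reported in the same way over [window stated by the sponsor]. Comparisons of categorical variables between named groups are exploratory and use Pearson's chi-square, or Fisher's exact test when expected counts are small.

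The two-sided version must be named because the exact versions differ. The equal-tailed one always agrees with the Clopper-Pearson interval. For the secondary endpoint, the natural source for the window is the follow-up sentence: "Patients were followed up for 6 months from the end of prophylactic treatment for the occurrence of additional fungal infection and survival".

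**Cost.** A few lines of text and no new data. Clopper-Pearson is wider than Wilson, by 5.1 points at 6/20 (42.4 − 37.3) and 2.6 points at 12/40 (30.0 − 27.4). Relative to Pearson, the equal-tailed test loses little power at 30% (0.995 against 0.999 at n = 20; both near 1 at n = 40). It loses more if the true rate is nearer 80%, as the 60% column above shows. At n = 20 the probability-ordered exact test avoids that loss, but it can then disagree with the reported interval, as at 12/20.
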